#### 384 4.1.1 Management of control groups

385 Since not all treatments may be available or suitable for all patients, those in the 'no  
386 additional treatment' arm will only be included in a given comparison if, at the point of their  
387 randomisation, they *could* alternatively have been randomised to the active treatment of  
388 interest (i.e. the active treatment was available at the time and it was not indicated or contra-  
389 indicated). The same applies to any further treatment comparisons that may be added at a  
390 later stage; they will be compared only to those patients recruited concurrently.

#### 391 4.1.2 Adjustment for baseline characteristics

392 The main logistic regression analyses described above will adjust for important prognostic  
393 markers recorded at baseline (eg, age, RT-PCR Ct value, virus type, and time since  
394 symptom onset). This provides a safeguard against the impact that any chance imbalances  
395 in their frequencies between randomised groups may have on the randomised comparisons.  
396 In addition, even if there were no such imbalances, adjustment for baseline characteristics  
397 somewhat increases statistical power by ensuring that, effectively, better-prognosis patients  
398 are compared only with each other and that worse-prognosis patients are compared only  
399 with each other. [Exact details of the prognostic factors adjusted for in the logistic regression  
400 analyses will be provided in the SAP prior to any unblinded analyses being done.](#)

#### 401 4.1.3 Pre-specified subgroup analyses

402 Pre-specified subgroup analyses of the effects on the primary and secondary outcome will  
403 be conducted for each part of the main randomisation. Tests for heterogeneity (or tests for  
404 trend between 3 or more ordered groups) will be conducted to assess whether there is any  
405 good evidence that the effects in particular subgroups differ materially from the overall effect  
406 seen in all patients combined. The results of subgroup analyses will be interpreted with  
407 appropriate caution. In particular, due allowance for the number of such analyses will be  
408 made in the interpretation of the results noting that even if a treatment truly works similarly  
409 well in all patients, by chance it is highly likely that it will seem not to in some subgroups  
410 (and may even appear to be harmful). The following subgroups will be considered:

- 411 • Marburg or Ebola disease (and by virus strain e.g. MARV, RAVV, *EBOV*, *BDV*  
412 *SUDV*).
- 413 • Age ([children, younger adults, older adults](#)).
- 414 • *Filovirus* nucleoprotein cycle-threshold (Ct) value using quantitative RT-PCR from  
415 latest test conducted prior to randomisation ([high, low](#)).
- 416 • Number of days since symptom onset ([divided at the approximate median](#)).
- 417 • *Filovirus* vaccination status ([yes, no, unknown](#)).
- 418 • Randomised allocation in other completed factorial comparisons.

419 Further exploratory subgroup analyses will include:

- 420 • Severity of disease at time of randomisation on the basis of one or more of:

- 421 (a) Extent of physiological disturbance at the time of enrolment (e.g. qSOFA  
422 score in adults (0-1, 2 or more); or PEWS score in children (0-2, 3 or more).  
423 (b) Evidence of organ dysfunction at the time of enrolment (e.g. creatinine > 150  
424 umol/L; aspartate transaminase or alanine transaminase > 5 times the upper  
425 limit of normal).

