## 344 4 STATISTICAL ANALYSIS

345 All analyses for reports, presentations and publications will be prepared by the Statistical  
346 Analysis Team. [The purpose of this section is to describe the main statistical approaches to  
347 be used in the trial.](#) Additional technical details (e.g. cut points for subgroup analyses) will  
348 be defined by the Trial Steering Committee and Statistical Analysis Team prior to any  
349 unblinding of effects of study treatments and made publicly available (including any  
350 subsequent revisions) .

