### 784 8.4 Laboratory assays

[Paediatric](#) samples will be reduced in volume according to standard procedures. Standard  
care samples will be prioritised over research samples if volume reduction is required. Ability  
to take samples is dependent on staff availability, the availability of suitable laboratory  
facilities and caseload. Research samples may therefore be reduced or missed if needed  
to maintain care standards and staff safety, and to reflect the assays that can be performed  
by the laboratory attached to a treatment facility.

Samples will not be duplicated if they are collected on the same day for clinical reasons.

785 ***Filovirus* testing:** *Filovirus* RT-PCR are performed per local clinical laboratory protocols as  
786 part of standard care. The virus species tested will be dependent on the species responsible  
787 for outbreak at the time of testing. The results of these tests (quantitative result and assay  
788 used) will be recorded at baseline and each day subsequently (see section 6.8). Samples  
789 obtained for PCR are typically  $\leq 4$  ml whole blood in an EDTA tube. Finger or heel-pricks of  
790 blood on a dry swab are sometimes obtained when venepuncture is not possible.

791 **Malaria testing:** Malaria diagnostic tests are performed on the triage blood sample as part  
792 of standard care. The result will be recorded at baseline.

793 **Pregnancy testing:** For women of childbearing age (15-49 years) a  $\beta$ HCG test is performed  
794 on the triage blood sample as standard of care. Urine testing is also acceptable. The result  
795 will be recorded at baseline. [A further test will occur at discharge or day 28 \(which ever](#)  
796 [comes earliest\)](#) as a study specific sample.

797 **Biochemistry:** Creatinine, AST, and ALT will be collected at baseline and days 3,5,7,10 per  
798 local clinical laboratory protocols.

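### Effect modification by Ct and by days since symptom onset is tested only between two groups, which discards roughly a quarter to a half of the information in two numeric variables

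*Protocol*

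**What the plan says.** Section 4.1.3 lists the subgroup variables. One is "nucleoprotein cycle-threshold (Ct) value using quantitative RT-PCR from" the "latest test conducted prior to randomisation ([high, low" groups; another is "Number of days since symptom onset", "divided at the approximate median". The planned tests are for heterogeneity, or for "trend between 3 or more ordered groups) will be conducted to assess whether there is any" difference from the overall effect. Age has three ordered groups and so qualifies for a trend test. Ct and symptom duration have two each, so for them a trend test adds nothing.

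The opening of section 4 leaves some matters for later: "Additional technical details (e.g. cut points for subgroup analyses) will" be settled before unblinding. That defers where to cut, not whether to cut.

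Section 6.4 records the date of symptom onset and the Ct value of the latest test. Section 8.4 says that "RT-PCR are performed per local clinical laboratory protocols as" part of standard care and that the species tested depends on the outbreak. It also says what is kept: "The results of these tests (quantitative result and assay" used.

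**The concern.** A SAP that follows section 4.1.3 would test whether the treatment effect depends on viral load, or on time since onset, by comparing two halves. Every patient in a half is then treated as alike, whether just beyond the cut or far from it. If the effect changes gradually, this throws away information that the trial already holds.

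The question is a natural one for this trial. Section 4.2 says the numbers needed depend on how far the proportional mortality reduction differs between better- and worse-prognosis patients, and its small-trial example ties prognosis to Ct. Section 5.1 asks the Data Monitoring Committee to look at the section 4.1.3 subgroups as well as the overall result. Interaction tests are weak at the sample sizes in view, so an avoidable loss matters more here than it would for the main effect.

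**Working it through.** **1. The plan's own figures.** The protocol gives no power for subgroup tests. Its main figures (section 4.2) reproduce. With 260 per arm, 50% v 33.3% at 2P=0.01 gives 90.3% power, and 50% v 37.5% at 2P=0.05 gives 82.1%. In the 120-patient example, deaths are 3 v 9 and 21 v 27 among 30 v 30 in each stratum. Observed minus expected is −3 + −3 = −6. The variance is 2 × (30·30·12·48)/(60²·59) = 4.88. So z = −6/2.21 = −2.72 and 2P = 0.0066, as claimed (<0.01).

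**2. Information kept by a two-group split.** For a linear interaction, the efficiency of the split relative to the continuous variable is the squared correlation between the variable and its split indicator. For a normal variable cut at quantile q, with c = Φ⁻¹(q), this is φ(c)²/[q(1−q)]. At the median it is 0.3989²/0.25 = 0.637 = 2/π. The loss is 36%, and equal power needs 1/0.637 = 1.57 times the patients.

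The documents give no distribution for either variable and no Ct cut, so a range is needed:

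| Case (assumed) | Kept | Lost |
|---|---|---|
| Uniform, median cut | 75% | 25% |
| Normal, median cut | 64% | 36% |
| Normal, 40/60 cut | 62% | 38% |
| Normal, 30/70 cut | 58% | 42% |
| Normal, 20/80 cut | 49% | 51% |
| Gamma, shape 4, median cut | 59% | 41% |
| Gamma, shape 2, median cut | 55% | 45% |
| Exponential, median cut | 48% | 52% |

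The skewed cases are the more plausible ones for symptom days. Ordered thirds with a trend score would keep 79% for a normal variable.

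**3. Effect on power (two-sided 0.05).** Power on the split = Φ[(1.960 + z_power)·√efficiency − 1.960].
- 80% on the continuous value, efficiency 0.637: 2.802 × 0.798 − 1.960 = 0.276, giving 61%.
- 90%, efficiency 0.637: 3.242 × 0.798 − 1.960 = 0.626, giving 73%.
- 80%, efficiency 0.75: 2.802 × 0.866 − 1.960 = 0.466, giving 68%.
- 80%, efficiency 0.48: 2.802 × 0.693 − 1.960 = −0.019, giving 49%.

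**4. Simulation.** Logistic model, N = 520, 1,500 runs, normal covariate with prognostic slope 1.2 per SD and treatment log odds ratio −0.7 at the mean (all assumed except N). For interaction slopes of 0.4, 0.6 and 0.8 per SD, power was 30%, 52% and 75% on the continuous value and 21%, 36% and 50% on the median split. With no interaction, rejection rates were 4.3% and 5.5%. Putting the continuous powers through step 3 predicts about 20%, 36% and 55%, so the formula is close, and slightly optimistic at the largest slope.

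**5. Assay differences (illustration only).** Assume normal Ct, within-assay SD of 4 to 6, half the patients on a second assay, and one common cut at the pooled median. An offset of 1 cycle then puts 3–5% of patients in the wrong half, and an offset of 4 cycles 13–19%. With assay-specific cuts the figure is zero. Over the same cases, uncorrected continuous Ct keeps 80% to 99% of the information and the split 50% to 63%. The continuous test is better throughout, but it does not by itself remove the offset.

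**The case against.** Two-group subgroups with a heterogeneity test are common and easy to read, and section 4.1.3 itself asks for cautious interpretation. The linear interaction is an assumption: if benefit changes abruptly at some Ct value, a split near that value can beat a linear term. The loss also depends on distribution and cut point. All of this stands. It is why the size is given as a range, why a non-linearity check belongs in the fix, and why it would be wrong to call the planned test the weakest possible; a more uneven split would do worse.

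Three stronger readings are tempting but not supported.

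- A reader might infer that a single Ct cut is imposed across assays and that patients are therefore misplaced. No section says so. Section 4 defers cut points and section 8.4 records the assay, so cuts by virus or assay remain open. The documents give neither a Ct spread nor an offset between assays, so step 5 only illustrates what could follow.
- A reader might take the 30% and 90% mortality example in section 4.2 as evidence that Ct modifies the effect. The odds ratio is (0.10/0.90)/(0.30/0.70) = 0.26 in one half and (0.70/0.30)/(0.90/0.10) = 0.26 in the other. On the scale of the planned logistic model the example shows Ct as prognostic, with no interaction.
- A reader might think that the primary result or the stopping guidance is weakened. Ct enters the primary model as a baseline covariate whose details section 4.1.2 leaves to the SAP. The benchmark in section 5.1 is 3 standard errors on mortality, not an interaction test. The committee also needs effects within groups, which the split supplies.

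**Conclusion.** The point holds as a minor one. Section 4.1.3 fixes both numeric modifiers as two-group tests, and the deferral of cut points does not undo that. For a roughly linear interaction, a normal variable and a median cut, about 36% of the information is lost and 80% power becomes about 61%. Over the other cases tried, with cuts no more uneven than 20/80, the loss is about 25% to 52%, and 80% power becomes about 68% to 49%. These figures rest on assumed distributions and a smooth trend. They concern the subgroup tests only. How many patients a common Ct cut would misplace, if one were used, cannot be established from the documents.

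**What to change.** In section 4.1.3, state that the interaction tests for Ct and for days since symptom onset use the continuous value, through a treatment-by-covariate term with a check for non-linearity. State also that the two-group estimates are kept for display and for the Data Monitoring Committee. Add that the Ct test accounts for the recorded virus and assay, for example by a sensitivity analysis with Ct standardised within virus and assay. A sensitivity analysis is preferable to a mandatory transformation: virus, assay and outbreak may largely coincide, and standardising could then remove real differences in viral load between outbreaks. How Ct enters the primary model can stay with the SAP.

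The cost is two or three sentences and little analysis work, with no new data and no burden on sites. The main downside is that the continuous test assumes a smooth trend; rarely used assays will also need grouping. Section 4.1.3 covers the secondary outcome too, which section 4.1 analyses by a Wilcoxon rank-sum test. That test has no ready covariate term, so the SAP should name a method for it or keep the two-group comparison there. If grouping is preferred throughout, ordered thirds with the trend test that section 4.1.3 already allows would recover part of the loss.

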#### 426 4.1.4 Allowance for multiple comparisons

427 The mortality results for 1:1 comparisons in the factorial design are uncorrelated with any  
428 other results and will therefore be reported without formal adjustment for multiple testing.  
429 Throughout, due allowance for the number of analyses (including of secondary and other  
430 outcomes and of effects in subgroups) will be made in interpreting the results.

#### 431 4.2 Sample size estimation

432 The larger the number randomised, the more accurate and informative the results will be  
433 and, over time, the more potential treatments can be assessed. However, it is not possible  
434 to make precise sample size estimates in the context of an outbreak where there are many  
435 unknowns. The numbers required will be influenced by many factors, including the case  
436 fatality and speed of presentation and diagnosis at a clinical facility, changes in usual  
437 standard of care, and how much the proportional reduction in mortality differs between  
438 better-prognosis and worse-prognosis patients.

439 Ideally, each comparison should be sufficiently large to provide good power (e.g. 90% power  
440 to achieve  $2P=0.01$ ) to detect a proportional reduction in mortality of at least one third. This  
441 may require randomisation of several hundred patients in each comparison. For example, if  
442 mortality in the reference arm was 50%, randomisation of around 520 participants in  
443 a single comparison would give more than 90% power at  $2P=0.01$  to detect a proportional  
444 reduction in mortality of one-third and more than 80% power at  $2P=0.05$  to detect a smaller  
445 (but still useful) reduction in mortality of one-quarter. (Note that with 50% mortality in the  
446 reference arm, the above mortality risk reductions of one-third or one quarter would  
447 represent mortality odds reductions of, respectively, one-half or two-fifths.)

448 However, it is possible that any single outbreak might end before the trial has recruited such  
449 numbers during that outbreak, or in some instances, that availability of some of the study  
450 interventions will limit enrolment. Even these more limited numbers, perhaps from a single  
451 outbreak, might still deliver clear results and change clinical practice. Suppose, for example,  
452 that 120 patients were randomised between a monoclonal antibody plus usual care vs. usual  
453 care alone. The primary analysis of the effects of adding the antibody to usual care would  
454 then be based on only 60 vs 60 patients, far fewer than ideally needed. Nevertheless,  
455 suppose that the antibody reduced 28-day mortality from 30% to 10% in the better-prognosis  
456 half of all patients and from 90% to 70% in the worse-prognosis half (approximately as was  
457 seen for patients with high and low RT-PCR Ct values with two successful antibodies to  
458 EBOV in the PALM trial in eastern DRC). Combining the results from 2x2 analyses within  
459 each of these two prognostic strata would then yield clear evidence of benefit at  $2P<0.01$ .

460 This does not mean that 120 patients is the ideal trial size, but it does indicate that useful  
461 information *could* emerge from even quite a small trial and may be achievable in a single  
462 outbreak. If this trial, or some parts of it, extends over multiple outbreaks in various locations,  
463 it could eventually include substantial numbers and address additional questions.

#### 464 4.2.1 Review and potential to modify sample size

465 Throughout the trial, the Trial Steering Committee, blind to information about the effects of  
466 ongoing treatment comparisons, will monitor event rates (both overall and by groups with  
467 different prognoses) to determine whether, in its view, sufficient participants have been  
468 randomised in each comparison. For instance, if the blinded mortality rate turns out to be  
469 much lower than anticipated in section 4.2, then the TSC may decide to increase the number  
470 of patients in order to achieve the desired power to detect a mortality risk reduction of one  
471 third. At the end of an outbreak, for each comparison the Trial Steering Committee may elect  
472 to: (a) close it and report the unblinded results; or (b) pause it (remaining blind to the results)  
473 with a view to re-opening it in the case of a new outbreak. In this context, it is recognised  
474 that some potential treatments may only be relevant for MARV, SUDV or EBOV infections  
475 (e.g. a particular monoclonal antibody) whilst others may be relevant for a broad range of  
476 patients with Filovirus Disease regardless of the particular virus (e.g. host-directed  
477 immunomodulatory treatments).

478

## 479 **5 DATA MONITORING COMMITTEE (DMC) [ NOW SEPARATED ]**

480

481 During the study, interim analyses of all study data will be supplied in strict confidence to  
482 the independent DMC. The DMC will request such analyses at a frequency relevant to the  
483 emerging data from this and other studies. Further details of the roles and responsibilities of  
484 the DMC will be described in a Data Monitoring Committee Charter.

485 The DMC will independently evaluate these analyses and any other information considered  
486 relevant. The DMC will determine if, in their view, the randomised comparisons in the study  
487 have provided evidence on mortality that is strong enough (with a range of uncertainty  
488 around the results that is narrow enough) to affect national and global treatment strategies.

489 In such a circumstance, the DMC will inform the Trial Steering Committee who will be  
490 responsible for considering any amendments to the protocol and trial comparisons and for  
491 plans to make the results available to the public. Unless this happens, the Trial Steering  
492 Committee, Principal Investigator(s), study staff, investigators, study participants, funders  
493 and other partners including WHO and relevant Ministries of Health and pharmaceutical  
494 partners supplying study treatments will remain blind to the interim results until 28 days after  
495 the last patient has been randomised for a particular intervention arm (at which point  
496 unblinded analyses may be conducted for that comparison).

### 497 **5.1 Early stopping for benefit**

498 The DMC will advise the Trial Steering Committee if, in its view, the randomized  
499 comparisons in the study provide “proof beyond reasonable doubt” that one of the study  
500 treatments reduces the primary outcome of mortality. In making this determination, the DMC  
501 would be expected to consider both the results for the overall population and for important  
502 subgroups of patients (see section 4.1.3) Appropriate criteria of proof beyond reasonable  
503 doubt cannot be specified precisely, but in general a benefit of at least 3 standard errors in  
504 an interim analysis on the primary outcome would be needed to justify halting the study  
505 prematurely for efficacy. If, in the view of the DMC, the evidence is not sufficiently  
506 convincing to affect national and global treatment strategies, then it would not be expected  
507 to recommend stopping the trial for efficacy. This approach has the practical advantage that  
508 the number of interim analyses has a negligible impact on the final significance level at which  
509 the primary outcome is tested.

### 510 **5.2 Blinding**

511 This is an open-label study. However, while the study is in progress, access to tabular results  
512 by allocated treatment allocation will not be available to the research team, patients,  
513 [Ministries of Health, pharmaceutical partners supplying study treatments, or members of the](#)  
514 [Steering Committee](#) (unless the DMC advises otherwise).

## 515 6 STUDY PROCEDURES

### 516 6.1 Practical considerations

517 Detailed information on how to implement trial procedures will be provided in standard  
518 operating procedures. Trial operations will be embedded in routine clinical workflow where  
519 possible to maintain high levels of familiarity, reduce error, and minimise duplication of effort.

520 A focused approach to clinical data collection will be used in recognition of the resource-  
521 limitation and clinical demand that may occur at some participating sites, the infectious risks  
522 to healthcare workers with study procedures, and that the critical research question is  
523 whether these treatments improve survival in diseases with high mortality.

524 Country-specific modifications to this core protocol (e.g. due to differences in age of consent,  
525 or proxy consent regulations) are contained in the relevant annexes.

### 526 6.2 Identification

527 Potential participants will be identified from the point that the treating clinician in a  
528 participating clinical site is notified of a positive *Filovirus* RT-PCR result by the laboratory.  
529 Patients are eligible for enrolment at any point during their acute illness.

### 530 6.3 Consent

531 Informed consent must be obtained for each patient before enrolment into the study. To  
532 maximise the opportunity for potential participants to make their own decisions about  
533 participation prior to potential clinical deterioration, patients with suspected Filovirus Disease  
534 can be approached for consent, although they will not be enrolled in the study until laboratory  
535 confirmation of disease.

536 For children, consent will be sought from their parents or legal guardian. The age where a  
537 child is able to consent for themselves will adhere to legislation in the country of trial  
538 operation (provided in country-specific annexes). Where possible, children who are 10 years  
539 old or more will also be asked for assent.

540 If an adult patient cannot provide consent, reasonable attempts will be made to reach the  
541 next of kin to provide consent by proxy.

542 Proxy consent must be witnessed but may be obtained over the telephone if a  
543 parent/guardian or legally acceptable representative cannot be physically present (e.g. due  
544 to treatment unit visiting rules or parental quarantine, isolation, or illness).

545 Due to the severity of Filovirus Disease, patients who lack capacity to consent due to severe  
546 disease, and for whom a relative to act as the legally designated representative is not  
547 available, randomisation and consequent treatment will proceed with consent provided by a  
548 clinician (independent of the clinician seeking to enrol the patient and not connected with  
549 the conduct of the trial) who will act as the legally designated representative (if allowed by  
550 local regulations). If a participant subsequently regains capacity prior to discharge, they  
551 should be provided with information about the trial, their rights, and how to exercise them.  
552 Provision of such information should be documented in the medical record.

553 Consent will include provision for secondary use of data which includes use by the  
554 pharmaceutical partners that supply study treatments, regulators, public health and  
555 academic organisations.

